4.8.2 Laboratory test results

Blood and urine samples will be collected by site staff for clinical laboratory testing. Urine pregnancy tests will be performed at the site. All other samples will be analyzed at the central laboratory. For all samples collected, the following data will be recorded in the eCRF: test category (i.e., Hematology, Serum Chemistry, Urinalysis, Serum Pregnancy Test, Urine Pregnancy Test, or Urine Drug Screen), collection date, and the accession number. For urine pregnancy tests, the result will also be recorded in the eCRF as "POSITIVE" or "NEGATIVE".

Collected laboratory samples will then be processed at the central laboratory for the calculation of reported values for the laboratory tests shown in Table 3. Central laboratory data will include test category, lab test name, reported result, reported unit, reported reference range (i.e., low and high), International System of Units (SI) result, SI unit, SI reference range, and reference range indicator. The reference range indicator will be recorded as "NORMAL" or "ABNORMAL" for character results and as "NORMAL", "LOW", or "HIGH" for numeric results. Data from the central laboratory will be combined with the laboratory eCRF data prior to analysis.

Change from baseline values to each post-baseline assessment will be calculated for all continuous laboratory tests.

Test category	Tests assessed
Hematology	hemoglobin, hematocrit, red blood cell count, red blood cell indices, mean corpuscular hemoglobin, mean corpuscular hemoglobin concentration, mean corpuscular volume, platelet count (or estimate), white blood cell count including differential
Serum chemistry	albumin, total bilirubin, total protein, calcium, alkaline phosphatase, alanine aminotransferase, aspartate aminotransferase, blood urea nitrogen, creatinine, creatine kinase, glucose, sodium, potassium, chloride, bicarbonate, lactate dehydrogenase, uric acid, thyroid stimulating hormone ¹ , T4 ¹
Urinalysis	pH, specific gravity, blood, glucose, protein, ketones
Pregnancy test ²	serum, urine
Urine drug screen	amphetamines, barbiturates, benzodiazepines, cocaine, opiates, phencyclidine, cannabinoids, propoxyphene, methadone

Table 3: Laboratory test categories and tests assessed

¹ Screening only

² Females only

4.8.3 Vital sign results

The following vital sign data will be recorded in the eCRF: assessment date, height, weight, temperature, temperature measurement method, pulse rate, respiratory rate, systolic blood pressure (BP), and diastolic BP. The temperature measurement method will be recorded as "Oral" or "Tympanic".

Change from baseline values to each post-baseline assessment will be calculated for pulse rate, respiratory rate, systolic BP, and diastolic BP. Potentially clinically important (PCI) flags will be derived for systolic BP, diastolic BP, pulse rate, respiratory rate, and change in body weight (see Table 4).

Table 4: Potentially clinically important criteria for vital sign results

Vital sign measure	Lower PCI criterion	Upper PCI criterion
Pulse rate	\leq 50 bpm	≥130 bpm
Systolic BP	<90 mmHg	>130 mmHg
Diastolic BP	<50 mmHg	>85 mmHg
Change in Systolic BP	decrease \geq 30 mmHg	increase \geq 30 mmHg
Change in Diastolic BP	decrease $\geq 20 \text{ mmHg}$	increase $\geq 20 \text{ mmHg}$
Change in body weight	decrease $\geq 7\%$	increase ≥7%

BP = blood pressure; PCI = potentially clinically important

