1 OVERVIEW

This Statistical Analysis Plan (SAP) describes the planned analysis and reporting for Aevi Genomics Medicine Protocol AEVI-001-ADHD-202 (A Multicenter, 2-Part, 6-Week, Double-blind, Randomized, Placebo-controlled, Paralleldesign Study to Assess the Efficacy and Safety of AEVI-001 in Children and Adolescents [Ages 6-17 Years] with Attention Deficit Hyperactivity Disorder and with or without Copy Number Variants in Specific Genes Implicated in Glutamatergic Signaling and Neuronal Connectivity), Final Version 7.0 dated 25 July 2018. This SAP is for Part A of the study only; a separate SAP will be prepared for Part B.

The statistical analyses and summaries described in this SAP will follow the International Conference on Harmonization of Technical Requirements for Registration of Pharmaceuticals for Human Use (ICH) guideline for Statistical Principles for Clinical Trials (ICH E9 Expert Working Group, 1999) and will form the basis of the results sections of the clinical study report (CSR) in accordance with the ICH guideline for Structure and Content of Clinical Study Reports (ICH Harmonised Tripartite Guideline E3, 1995). This SAP will be finalized and signed-off before database lock and unblinding of treatment codes. Any changes to the analyses that are not included in this SAP will be documented in the CSR.

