2.3 Determination of sample size

For Part A of the study, 42 unique subjects are planned to be randomized to yield approximately 34 subjects who provide post-baseline efficacy data on the primary endpoint. Assuming an effect size of 1.0, this number will yield approximately 80% power to detect a significant difference in mean change from baseline for the ADHD-RS-5 total score at Visit 8 (Week 6) between the treatment groups, based on a 2-tailed test with $\alpha = 0.05$ and 1:1 randomization. In Part A of the study, an interim analysis will be performed when approximately 75% of randomized subjects have completed the study. The sample size could be increased to 64 randomized subjects.

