4.3 Demographics and other baseline characteristics

4.3.1 Age

The date of consent and date of birth will be recorded in the IRT system. In addition, age at informed consent in years and age stratum will be derived within the IRT system. Age stratum will be derived at randomization based on the subject's age at informed consent. Table 1 shows the stratum codes and descriptions assigned to subjects in Part A. Prior to analysis, all age-related data recorded or derived in the IRT system will be transferred into the eCRF.

Table 1: Age stratum codes and descriptions for Part A

Stratum code	Stratum description
1	Age at informed consent 6 to 12 years old, Part A
2	Age at informed consent 13 to 17 years old, Part A

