5.3 Primary efficacy analysis

The change from baseline in ADHD-RS-5 total score will be analyzed with mixed model repeated measures (MMRM) methods using the full analysis set. The model will include derived visit (see Section 4.7), age stratum, treatment group, and treatment-by-visit interaction as fixed factors and baseline ADHD-RS-5 total score as a covariate. Robust variance estimates for the fixed effects will be used for testing treatment differences. Within subject variability will be modeled using an unstructured (i.e., TYPE = UN) covariance pattern. In case of convergence problems, a banded Toeplitz (i.e., TYPE = TOEP(5)) structure for the covariance pattern will be used. The comparison of interest will be the difference between the AEVI-001 and placebo treatment groups at Visit 8. Model based point estimates (i.e., least square [LS] means for each treatment group and the treatment difference), 95% confidence interval for the difference, p-value, and effect size will be reported for each derived visit. Effect size will be calculated as the LS mean difference divided by an estimate of the pooled standard deviation.

Similar MMRM methods will be used to test for treatment differences in each CNTN4 CNV subgroup (see Section 4.3.8 for definition of CNTN4 CNV indicator). To control the overall type I error rate for these subgroup comparisons, a hierarchical testing procedure will be used with comparisons of the primary efficacy variable tested in the following fixed sequence:

- Full analysis set
- Full analysis set CNTN4 CNV subgroup
- Full analysis set Non-CNTN4 CNV subgroup

Supportive MMRM analyses of the primary endpoint will also be performed using the PP analysis set.

Descriptive statistics for the ADHD-RS-5 total score and change from baseline in ADHD-RS-5 total score will be presented by treatment group and derived visit. A similar descriptive statistics display will also be presented by CNTN4 CNV indicator and age stratum.

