5.5 Safety analyses

For all safety endpoints, descriptive statistics will be presented by treatment group and visit (where applicable) using the safety analysis set. In addition, some safety endpoints may be further summarized by optimized dose (see Section 4.6). In summaries of change from baseline safety variables, only subjects with both baseline and post baseline data will be included. No formal hypothesis tests will be performed for any safety endpoint.

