5.5.2.1 TEAEs

The incidence of TEAEs will be summarized by treatment group, system organ class (SOC), and preferred term. Each subject will be counted only once per SOC and preferred term. An additional display may be produced by treatment group and preferred term.

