5.5.4 Vital sign results

Descriptive statistics for all reported values and change from baseline values will be summarized by treatment group and visit. Only the original assessment for each visit will contribute to these summaries; repeat or unscheduled assessments will not be included in the calculation of descriptive statistics by visit. The number and percentage of subjects with PCI values at any time will be tabulated by treatment group. Summaries of PCI values will include all assessments regardless of whether an original, repeat, or unscheduled assessment. All vital sign results data will be listed by subject and visit.

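### SAP Table 4's single upper blood-pressure limits exceed the protocol's entry limit in every cell for ages 6 to 12; an added descriptive count by age stratum would be a cheap gain in sensitivity

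*SAP*

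**What the plan says.** SAP 4.8.3 defines potentially clinically important (PCI) flags in "Table 4: Potentially clinically important criteria for vital sign results". The upper limits are above 130 mmHg systolic and above 85 mmHg diastolic. Separate change rows flag a rise of at least 30 mmHg systolic or 20 mmHg diastolic. None of these depends on age, sex or height.

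SAP 5.5.4 then states: "The number and percentage of subjects with PCI values at any time will be tabulated by treatment group". Repeat and unscheduled readings count. No split by age is named. For safety generally, SAP 5.5 offers only that "some safety endpoints may be further summarized by optimized dose", and it plans no hypothesis test.

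The age stratum (6 to 12, 13 to 17) is already available. SAP 4.3.1 says "Age stratum will be derived at randomization", using age at consent, and SAP 5.3 uses it for the ADHD-RS-5 total score: "A similar descriptive statistics display will also be presented by CNTN4 CNV indicator and age stratum".

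Protocol 8.5.2, exclusion criterion 10, bars a subject whose blood pressure is above the 95th percentile for age, sex and height at Visit 1 and/or Visit 2. Protocol Section 20 prints those values and gives the look-up rule.

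On scope, SAP 1 says "This SAP is for Part A of the study only". Part A plans 42 randomised subjects, and SAP 2.3 adds that "The sample size could be increased to 64 randomized subjects".

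**The concern.** The trial carries two yardsticks for the same measurement. One adapts to the child's age, sex and height; the other is a single pair of numbers. For a young child the fixed limit may be so far above the entry limit that a clear post-dose rise never reaches the PCI table.

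Vital signs are part of a stated safety objective, and the sample includes children aged 6 to 11, whereas the earlier placebo-controlled study described in Protocol 6.2 enrolled ages 12 to 17. A low PCI count among the youngest could partly reflect the chosen cut-off. A table pooled over ages would not show this.

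**Working it through.** The plan gives no calculated figure on this point, so the check starts from the protocol's printed tables.

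**Inputs**
- Fixed limits and change criteria from SAP Table 4: 130/85 mmHg; rise of at least 30/20 mmHg.
- Entry limits from Protocol Section 20: two sexes, 12 years of age, seven height columns, systolic and diastolic.
- Some cells are garbled in the text read from PDF and were restored from their neighbours (for example 1111 as 111, 92 as 76, 98 as 86). None sets a minimum or maximum at ages 6 to 12.

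**Step 1: ages 6 to 12.** Gap = fixed limit minus entry limit. Cells: 2 sexes x 7 ages x 7 columns = 98 per measure.

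| | Entry limit, boys | Entry limit, girls | Gap, boys | Gap, girls | Median gap | Cells with fixed limit higher |
|---|---|---|---|---|---|---|
| Systolic | 109-127 | 108-126 | 3-21 | 4-22 | 12.5 | 98 of 98 |
| Diastolic | 72-83 | 72-82 | 2-13 | 3-13 | 7 | 98 of 98 |

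The gap is at least 10 mmHg in 73 of the 98 systolic cells and at least 5 mmHg in 81 of the 98 diastolic cells.

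**Step 2: do the change rows close the gap?** The highest reading with no flag is min(130, baseline + 29) systolic and min(85, baseline + 19) diastolic. Subtracting the entry limit gives the unflagged excess. The documents give no baseline blood pressure, so the distance of baseline below the entry limit is an assumption:

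| Assumed distance below entry limit (mmHg) | 0 | 10 | 20 | 30 |
|---|---|---|---|---|
| Largest unflagged excess, systolic | 22 | 19 | 9 | none |
| Largest unflagged excess, diastolic | 13 | 9 | none | none |

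The excess is zero in every cell only when baseline lies at least 29 mmHg (systolic) or 19 mmHg (diastolic) below the limit.

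Mid-table example: a girl aged 9 at the 50th height percentile has an entry limit of 117/77. With an assumed baseline 10 mmHg lower (107/67), the change rows start at 107 + 30 = 137 and 67 + 20 = 87, beyond the fixed limits. Readings of 118 to 130 systolic or 78 to 85 diastolic carry no flag. For a boy (118/79) the ranges are 119 to 130 and 80 to 85.

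**Step 3: ages 13 to 17.** Cells: 2 x 5 x 7 = 70 per measure.

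| Entry limit against fixed limit | Above | Equal | Below |
|---|---|---|---|
| Systolic: boys + girls | 18 + 5 = 23 | 3 + 3 = 6 | 14 + 27 = 41 |
| Diastolic: boys + girls | 7 + 2 = 9 | 4 + 6 = 10 | 24 + 27 = 51 |

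The entry limit exceeds the fixed limit by up to 10 mmHg systolic and 4 diastolic in boys, and by 2 and 1 in girls. All seven systolic cells for 17-year-old boys (131 to 140) are above 130, so a reading acceptable at entry can count as PCI. Three of the nine diastolic cells in the first column print as 98 and are read as 86.

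**Step 4: scale.** Per arm, 42/2 = 21 and 64/2 = 32. Stratum sizes are not given. Assuming 25%, 50% or 75% are aged 6 to 12, that stratum holds about 5, 10 or 16 per arm at 42 randomised and 8, 16 or 24 at 64.

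**The case against.** The strongest answer is that the two limits serve different purposes. The percentile governs eligibility at Visits 1 and 2, and nothing in either document asks PCI flags to match it. A reader might infer that the SAP contradicts the protocol, or that Table 4 is wrong for young children. The documents support neither; they show only that the limits differ. For the same reason it would be too strong to treat the entry limit as the correct on-treatment value and the fixed limit as a failure to meet it.

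A reader might also infer a distorted treatment comparison. That does not follow: both arms share the same limits, and randomisation is stratified by these age groups.

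Nor would a rise go unrecorded. Values and changes are summarised by visit and listed by subject (SAP 5.5.4). Changes the investigator judges clinically significant become adverse events (Protocol 10.3.3.2), and "The incidence of TEAEs will be summarized by treatment group, system organ class (SOC), and preferred term". The PCI table already goes beyond the by-visit descriptive summaries of Protocol 14.3.5.3.

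Finally, the largest excesses need a baseline close to the entry limit and the widest-gap cells, at age 6. At age 12 the gaps are 3 to 11 mmHg systolic and 2 to 7 diastolic.

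All of this stands and limits the weight of the point. It does not remove it: the PCI count is the SAP's own categorical summary of blood pressure, and it is less sensitive to readings above the entry limit in the younger stratum. Splitting the existing count by age would show where flags occur but would not register any of the unflagged readings.

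**Conclusion.** The point holds as an optional, low-cost improvement to a descriptive safety display in Part A. At ages 6 to 12 the fixed limits lie above the entry limit in all 196 cells, by 3 to 22 mmHg systolic and 2 to 13 diastolic. The change criteria cover the difference fully only for baselines at least 29/19 mmHg below the entry limit. At ages 13 to 17 the relation is mixed.

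The cell comparison rests on the printed tables, with garbled cells read from context. The unflagged excesses rest on assumed baselines, and the stratum sizes on assumed age mixes. How many subjects would be affected cannot be estimated from the documents. No efficacy result, sample size, power or alpha is touched.

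**What to change.** Keep all Table 4 criteria and add to SAP 5.5.4:

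*The number and percentage of subjects with any post-dose systolic or diastolic BP above the 95th-percentile value in the Protocol Section 20 tables (age at informed consent, sex, screening height, Protocol Section 20 height-column rule) will be tabulated by treatment group and age stratum (6-12, 13-17). All post-dose assessments, including repeat and unscheduled ones, will be included, as for the PCI summaries. This is a comparison with the entry limit and not a clinical threshold.*

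Show the existing blood-pressure PCI counts by age stratum beside it. Age at consent keeps every subject within the printed rows, including one who turns 18 on study.

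The cost is one split, one derivation and one display. Age stratum, sex and height are already collected. There are three downsides:
- The height percentile must be derived. Protocol Section 20 obtains it from web calculators based on CDC data and files it in source documents; that height-for-age reference is not printed, so the SAP should name the one used.
- A marginal exceedance at a single one of six scheduled post-dose visits, or at an unscheduled reading, will be counted.
- Cells are small. The counts help in reading the listings and support no inference.

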4.8.4 Electrocardiogram results

Standard 12-lead ECGs will be performed after the subject has been supine for approximately 5 minutes. All ECGs will be performed using the equipment supplied by the central ECG vendor. For all ECGs performed, the following data will be recorded in the eCRF: assessment date and time and the investigator interpretation of the ECG. The investigator assessment will be recorded as "Normal", "Abnormal - Not clinically significant", "Abnormal - Clinically significant", or "Unable to be evaluated".

Electronic ECG tracings will be analyzed by the central ECG vendor for the calculation of reported values for the following ECG tests: heart rate, RR interval, PR interval, QRS duration, QT interval, corrected QT interval using the Bazett formula (QTcB), corrected QT interval using the Fridericia formula (QTcF), and evaluator interpretation. ECG

vendor data will include ECG test name, reported result/finding, reported unit, standard result/finding, standard unit, and lead location. The evaluator interpretation result will be recorded as "NORMAL", "ABNORMAL", or "UNABLE TO EVALUATE". Data from the ECG vendor will be combined with the ECG eCRF data prior to analysis.

Change from baseline values to each post-baseline assessment will be calculated for heart rate, RR interval, PR interval, QRS duration, QT interval, QTcB interval, and QTcF interval. In addition, potentially clinically important flags will be calculated for heart rate, PR interval, QRS duration, QT interval, QTcB interval, QTcF interval, change from baseline in heart rate, and change in QT, QTcB, and QTcF intervals (see Table 5).

ECG measure	Lower PCI criterion	Upper PCI criterion
Heart rate	\leq 50 bpm	≥130 bpm
PR interval		\geq 180 msec
QRS duration		$\geq 100 \text{ msec}$
QT interval		\geq 450 msec
QTcB interval		\geq 450 msec
QTcF interval		\geq 450 msec
Change in heart rate	\leq 50 bpm & decrease \geq 5 bpm	
Change in QTcB	- •	increase \geq 30 msec
Change in QTcF		increase \ge 30 msec

ECG = electrocardiogram; PCI = potentially clinically important

4.8.5 Physical exam findings

The following physical exam data will be recorded in the eCRF: assessment date, body system, result, abnormal findings, and clinically significant flag.

- Result will be recorded as "NORMAL", "ABNORMAL", or "NOT DONE".
- Clinically significant flag will be recorded as "N" or "Y".

The abnormal findings and clinically significant flag variables are only recorded when the result is "ABNORMAL".

4.8.6 Columbia–Suicide Severity Rating Scale

The Columbia–Suicide Severity Rating Scale (C-SSRS; available at www.cssrs.columbia.edu) is a semi-structured interview that captures the occurrence, severity, and frequency of suicide-related thoughts and behaviors during the assessment period. The interview includes definitions and suggested questions to solicit the type of information needed to determine if a suicide-related thought or behavior has occurred. The C-SSRS has a "Baseline" version that will be completed at the Screening Visit (Visit 1) and a "Since Last Visit" version that will be completed at Visit 2 through Visit 8/ET. Both versions contain all 11 categories of suicidal ideation and behavior defined in the Food and Drug Administration (FDA) guidance document on suicidal behavior and ideation (FDA, 2012). Each category is assessed using a single question requiring a "Yes" or "No" response with follow-up questions for any "Yes" responses. The assessment date and each C-SSRS response will be recorded in the eCRF.

In addition, three C-SSRS composite indicator variables will be calculated as follows:

4.8.6.1 C-SSRS suicidal ideation indicator

A composite indicator of C-SSRS suicidal ideation will be calculated as:

- IF the response to any one of the five suicidal ideation questions is "Yes", THEN set the suicidal ideation indicator equal to 1.
- OTHERWISE, set the suicidal ideation indicator equal to 0.

4.8.6.2 C-SSRS suicidal behavior indicator

A composite indicator of C-SSRS suicidal behavior will be calculated as:

- IF the response to any one of the five suicidal behavior questions is "Yes", THEN set the suicidal behavior indicator equal to 1.
- OTHERWISE, set the suicidal behavior indicator equal to 0.

4.8.6.3 C-SSRS suicidal ideation or behavior indicator

A composite indicator of C-SSRS suicidal ideation or behavior will be calculated as:

- IF the response to any one of the 5 suicidal ideation questions or any of the 5 suicidal behavior questions is "Yes", THEN set the suicidal ideation or behavior indicator equal to 1.
- OTHERWISE, set the suicidal ideation or behavior indicator equal to 0.

5 ANALYSIS METHODS

All personnel involved in the conduct and analysis of the study will remain blinded to individual subject treatment assignments until the study has been completed, the data have been checked for accuracy with any errors corrected, and all analysis sets have been identified. Analysis will be carried out using SAS[®] (version 9.4 or newer, SAS Institute Inc, Cary, NC). Templates for the summary tables, figures, and subject data listings will be available separately. Data listings will include all data recorded for all enrolled subjects; where included in listings, data entered for screen failure subjects will be flagged.

Descriptive statistics for continuous data will include number of subjects (n), mean, standard deviation (SD), median, minimum, and maximum. Summaries of change from baseline variables will include only subjects who have both a baseline value and corresponding value at the timepoint of interest. Descriptive statistics for categorical data will include frequency and percentage. Calculation of percentages will exclude missing data as a category. Where appropriate, descriptive statistics may be presented with 95% confidence intervals (CIs). For analyses by visit (or derived visit; see Section 4.7), only the latest assessment for each visit will be used.

The minimum and maximum will be reported with the same degree of precision (i.e., the same number of decimal places) as the recorded data. Measures of location (e.g., mean and median) will be reported to 1 degree of precision more than the recorded data, and measures of spread (e.g., standard deviation) will be reported to 2 degrees of precision more than the recorded data.

Any changes to the analyses that are not included in this SAP will be documented in the CSR.

